15.6. Additional Efficacy Analyses

Analyses of changes in liver stiffness (TE) and liver fibrosis (ELF [HA, P3NP, and TIMP-1]) will be summarized and analyzed using the same methodology specified for the key secondary analyses of change in bilirubin.

The following clinical endpoints will be captured in the study:

- Time to death (all cause)
- Time to liver-related death
- Time to liver transplant
- MELD score ≥ 15 (for patients with MELD ≤ 12 at baseline)
- Hospitalization (as defined by a stay of 24 hours or greater) for new onset or recurrence of:
 - Time to variceal bleed
 - Time to hepatic encephalopathy (as defined by a West Haven score of ≥ 2)

- Time to spontaneous bacterial peritonitis (confirmed by diagnostic paracentesis)
- Time to uncontrolled ascites (diuretic resistant ascites requiring therapeutic paracentesis at a frequency of at least twice in a month).

The incidence and time to first occurrence of any above listed clinical events will be summarized by treatment group using the log rank test stratified by the randomization stratification factor. KM estimates of the distribution of the time-to-event will be tabulated and graphed by treatment group. The tabulation will include the KM methodology using 25th, 50th (median), and 75th percentiles with associated 2-sided 95% confidence intervals (CIs), as well as percentage of censored observations. The number and percent of patients censored and with events will be presented. The hazard ratio and 2-sided 95% CI will be estimated based on a Cox regression model stratified by randomization strata.

In addition, the incidence and time to each of the above clinical events, and the incidence and time to occurrence of hepatocellular carcinoma (HCC) will be summarized by treatment group using the same methods as defined above.

Full details regarding additional efficacy analyses will be detailed in the SAP.

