9.4. Randomization and Blinding

9.4.1. Methods of Assigning Patients to Treatment Groups

This study will be conducted in a double-blind, placebo-controlled manner. Enrolled patients who meet all eligibility requirements will be randomized in a 1:1 ratio to 1 of 2 treatment groups: placebo or OCA based on a predefined randomization code (generated by Sponsor or designee) using an interactive web response system (IWRS), which the Sponsor intends will serve as a computer-based patient registration system at Screening and Day 1.

Randomization will be stratified by CP class (CP-B or CP-C). Baseline MELD scores will be monitored on an ongoing basis to ensure adequate distribution of MELD scores. The IWRS will serve as the investigational product inventory and management system and may be integrated with the study database.

The Investigator or designee will be required to register the patient in the IWRS and may be prompted to provide patient data necessary to properly randomize and allocate the patient to treatment. A randomization number will be assigned and investigational product (OCA or

placebo) dispensing information will be provided (eg, bottle numbers allocated) while maintaining the study blind.

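### Kaplan-Meier curves and percentiles for the component events and HCC overstate absolute risk, because a death without the component can only be counted as censored

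*Protocol*

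**What the plan says.** Section 15.6 lists the clinical endpoints: all-cause death, liver-related death, transplant, MELD of 15 or more (for patients at 12 or less at baseline), hospitalization for variceal bleed, encephalopathy or spontaneous bacterial peritonitis, and uncontrolled ascites. For time to the first of these it states: "KM estimates of the distribution of the time-to-event will be tabulated and graphed by treatment group", with 25th, 50th and 75th percentiles. It then adds: "The number and percent of patients censored and with events will be presented".

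The components and HCC follow the same rule. The sentence that begins "In addition, the incidence and time to each of the above clinical events, and the incidence and time to occurrence of hepatocellular carcinoma (HCC" ends by saying that all of these "will be summarized by treatment group using the same methods as defined above". The opening of Section 15 also names KM for time-to-event data in general. Neither section mentions a competing-event state or a cumulative incidence estimator.

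For the treatment comparison: "The hazard ratio and 2-sided 95% CI will be estimated based on a Cox regression model stratified by randomization strata". The only randomization stratum is Child-Pugh (CP) class (Section 9.4.1).

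Section 15.6 closes by leaving full details of the additional efficacy analyses to the SAP, which is not at hand. Section 5.4.1 makes clinical outcomes an additional objective that the study is not designed to evaluate formally, and Section 15 rules out formal hypothesis testing.

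**The concern.** Death makes every later component event impossible. With only two states, a patient who dies without the component is either counted as having it, which changes the endpoint, or is censored. Censoring assumes that the patient stays at risk like those still alive. One minus KM then estimates the risk if nobody died first, and this exceeds the proportion who actually have the event. The KM percentiles come too early for the same reason.

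Section 5.4.4 expects many clinical events in this advanced population and treats placebo as their comparator. Section 7.1.3 lets double-blind follow-up run to about 3 years. A reader weighing benefit and risk would naturally read a component curve as absolute risk. If mortality differs between arms, the overstatement differs too, so the visual comparison of absolute risks can also mislead.

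**Working it through.** **Inputs from the protocol.** Estimator, two states, and same methods for components and HCC: Section 15.6. Follow-up: at least 48 weeks, up to about 3 years (Section 7.1.3). The protocol states no event rate, so it has no figure to reproduce.

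**Assumptions.** Annual risk 5-15% for a component taken alone and 5-40% for competing events; constant, independent hazards, λ = −ln(1 − annual risk).

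**Formulas.** With λE for the component, λC for competing events and follow-up T in years:
- KM with competing events censored: 1 − exp(−λE·T)
- Actual cumulative incidence (CIF): λE/(λE + λC) × [1 − exp(−(λE + λC)·T)]

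**One case in full.** Component 10%, competing 25% per year: λE = 0.1054, λC = 0.2877, sum 0.3930. At T = 3, one minus KM is 1 − 0.9³ = 27.1%. The CIF is (0.1054/0.3930) × [1 − exp(−1.179)] = 0.268 × 0.692 = 18.6%. The excess is 8.5 points.

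**Range** (excess from unrounded values; 48 weeks = 48/52 year):

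| Component / competing, per year | 48 weeks: 1−KM, CIF, excess | 3 years: 1−KM, CIF, excess |
|---|---|---|
| 5% / 5% | 4.6%, 4.5%, 0.1 | 14.3%, 13.2%, 1.0 |
| 10% / 15% | 9.3%, 8.6%, 0.7 | 27.1%, 21.7%, 5.4 |
| 10% / 25% | 9.3%, 8.2%, 1.1 | 27.1%, 18.6%, 8.5 |
| 10% / 40% | 9.3%, 7.4%, 1.9 | 27.1%, 14.4%, 12.7 |
| 15% / 40% | 13.9%, 11.2%, 2.8 | 38.6%, 20.9%, 17.7 |

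The first and last rows are the extremes of the grid.

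**Percentiles.** With hazards of 0.10 and 0.20 per year, the KM 25th percentile is −ln(0.75)/0.10 = 2.9 years. The CIF reaches 25% only when (1/3)[1 − exp(−0.30t)] = 0.25, at t = 4.6 years. It can never exceed 33%, so no median exists, although KM would imply one.

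**Arms with different mortality.** Take a component risk of 10% per year in both arms and competing risks of 10% and 30%. At 3 years, one minus KM is 27.1% in both arms, while the CIF is 23.4% and 17.1%. The equal KM curves correctly reflect equal cause-specific hazards, but they hide a 6.3-point difference in the proportion of patients who have the event.

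**The case against.** The strongest reply is that Section 15.6 defers detail to the SAP, which could add censoring rules and cumulative incidence. That is fair for the rules. It does not undo the estimator, because the protocol itself names KM curves and percentiles for each component and for HCC.

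Second, not every output is affected. A reader might infer that all component incidences will be too high. They will not: the number and percent with events are crude proportions, which censoring does not inflate. The log-rank test and Cox model remain valid for the cause-specific hazard. Competing death does not bias the composite, which includes death, or all-cause death. This objection stands and limits the point to the KM curves and percentiles.

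Third, the excess at 48 weeks is small, 3 years is the approximate outer duration, and every rate above is assumed. This also stands.

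A reader might infer that the plan censors patients at transplant. No sentence says so, and Section 7.4.3 keeps transplanted patients in scheduled visits. For transplant the rule is simply unstated.

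A reader might also fault the Cox model for omitting baseline MELD, since Section 9.4.1 says "Baseline MELD scores will be monitored on an ongoing basis to ensure adequate distribution of MELD scores". Stratifying the analysis as the randomization was stratified is standard and valid. In a simulation (25 per arm, 48 weeks, log hazard ratio 0.1-0.2 per MELD point, all assumed), omitting MELD caused no bias at a hazard ratio of 1. At a true 0.5, the median estimate was 0.50-0.55 without MELD and 0.50-0.53 with it. The standard error was 0.47-0.63 without and 0.48-0.65 with it. The event count matters far more: with 10 events the 95% limits are the estimate divided and multiplied by exp(1.96 × 2/√10) = 3.45.

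**Conclusion.** The point holds for the KM curves and percentiles of every component other than all-cause death, and for HCC. As described, they overstate absolute risk and give percentiles that are too early. Under the assumed rates and constant independent hazards, the overstatement is 0.1-2.8 points at 48 weeks and 1.0-17.7 points at 3 years. The direction follows from the estimator; the size depends on rates that the protocol does not give.

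The weight is minor: these are additional, descriptive endpoints with no formal test. But in a descriptive study the estimates are the result, and Section 5.4.1 intends the adjudicated events to feed a later joint evaluation with the outcomes study. It does not say that this hazard ratio is the quantity to be carried over, so no harm to that evaluation is shown through the Cox model.

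**What to change.** In Section 15.6 or the SAP:
- For each component other than all-cause death, and for HCC, replace the KM curves and percentiles with Aalen-Johansen cumulative incidence by arm, with 95% confidence intervals and death as a competing event.
- State that transplant is also a competing event for native-liver events, since transplanted patients remain in follow-up.
- Keep KM for all-cause death and the composite. Keep the crude counts, the stratified log-rank test and the CP-stratified Cox model, labelled as cause-specific for components.
- Optionally, as sensitivity analyses only, add baseline MELD to the Cox model and show the composite with and without the MELD component. Only patients at 12 or less at baseline can have that component, and their share may differ between arms by chance.

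The cost is a few sentences and a little standard programming. Death, transplant and event dates are already collected, so no new data are needed.

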15.7. Handling of Missing Data

Missing data will be assumed to be missing at random. No data will be imputed.

15.8. Data Monitoring Committee

An independent DMC includes hepatologists, pharmaceutical physicians, epidemiology/cardiology expert(s), and statistician(s) not involved in the study as Investigators, adjudication committee members, or consultants. The DMC will have oversight of the study conduct as defined by the DMC charter. All members will have considerable experience with clinical study conduct and DMCs. Any candidate found to have a conflict of interest or whose name is listed on the Food and Drug Administration (FDA) debarment list will not be offered membership. Conflicts of interest will be assessed regularly, and if members are found to have a new conflict of interest they will be replaced.

The DMC will meet approximately quarterly at scheduled meetings and ad hoc meetings will be convened, as appropriate, to review safety and efficacy data in order to ensure the safe and proper treatment of patients. Based on review of these data, the DMC will advise the Sponsor on the validity and scientific merit of continuing the study.

Written minutes of both the open and closed DMC sessions will be prepared. The closed minutes will be made available to the appointed Sponsor representatives only after the database is locked.

Data listings provided to the DMC do not contain individual patient treatment information; however, the DMC will have access to the database and may unblind individual patient data as appropriate. Summary tables reviewed by the DMC during closed sessions will include an overall column containing information regarding all patients and separate treatment columns with 'dummy' labels, ie, the actual treatment groups are used, but are not identified. Data reviewed during the meetings will include, at a minimum, disposition, demographics, exposure, clinical laboratory results, MedDRA-coded AEs, and AEs leading to early withdrawal of

investigational product. At each meeting, detailed narratives of interval SAEs (including events resulting in death) are reviewed by the DMC in addition to a cumulative list of all SAEs.

The DMC may agree to adjust meeting frequency based upon actual and projected safety and efficacy data availability. Adjustments to or stopping of the protocol defined doses may be considered based on DMC evaluation of OCA safety and tolerability.

All Investigators and responsible IRBs/IECs will be informed of any decisions made by the Sponsor based on recommendations from the DMC relating to patient safety, which alter the conduct of this study. The Investigators will inform the patients of such actions and the protocol, PIS, and ICF will be revised, as appropriate.

15.9. Adjudication Committees

All suspected liver-related clinical events, major adverse cardiovascular events (MACE)/expanded MACE, and drug-related hepatic injury events that occur after administration of the first dose of investigational product will be reviewed by the following blinded adjudication committees, depending on event type, before inclusion in any analysis. The 3 committees and event types they are responsible for adjudicating are as follows:

- Cardiovascular Adjudication Committee (CAC): Adjudicates all suspected MACE, including all deaths
- Hepatic Outcomes Committee: Adjudicates all deaths and suspected liver-related outcomes
- Hepatic Safety Committee: Adjudicates all suspected drug-related hepatic injury events

Each adjudication committee will have a charter that documents the reporting of events by the study site, definition of the suspected events to be adjudicated, supply of source documentation to the committee, entire data flow and process from committee membership, review of the events by the committee, reporting of the final assessment, and the working procedures of the committee.

The adjudication committee members will include experts with relevant adjudication experience; they will not be involved in the study as Investigators, DMC members, or consultants. Any candidate found to have a conflict or whose name is listed on the FDA debarment list is not offered membership. Conflicts of interest are assessed regularly, and if members are found to have a new conflict of interest they will be replaced.

The adjudication of suspected events will be based on available source documentation, including but not limited to individual clinical study data, hospital records, histology, discharge summaries, and/or death certificates. The adjudication committees will not receive any individual patient treatment or site-specific information. The assessment of events will be conducted in compliance with study-specific procedures, manuals, GCP, and all other applicable regulatory requirements, including the archiving of essential documents.

16. DIRECT ACCESS TO SOURCE DATA/DOCUMENTS

16.1. Study Monitoring

Study records at each site will be monitored at regular intervals by a representative of the Sponsor, the CRA. The role of the CRA is to aid the Investigator in the maintenance and documentation of complete, accurate, legible, well organized and easily retrievable data. In addition, the CRA will ensure the Investigator's understanding of all applicable regulations concerning the clinical evaluation of the investigational product and will ensure an understanding of the protocol, reporting responsibilities and the validity of the data. This will include ensuring that full and appropriate essential documentation is available.

In order to perform this role, the CRA must perform source data verification and as such must be given access to the patient's primary source documentation (eg, paper or electronic medical records such as consent to participate in the study, visit dates, screening and randomization numbers, demographic information, medical history, disease history, physical examination, vital signs, laboratory assessments [copy of laboratory reports], AEs, concomitant medications, dates of dispensing investigational product, ECGs, etc) that support data entries in the eCRF. The eCRF must be completed promptly after each visit to allow the progress and results of the study to be closely followed by the Medical Monitor.

The Investigator may exercise judgment in allowing the CRA access to particular sections of the patient's medical records if these are deemed irrelevant to the performance, observations or conduct of this study.

16.2. Audits and Inspections

The Investigator should understand that it may be necessary for the Sponsor, the IEC/IRB, and/or regulatory agencies to conduct one or more site audits during or after the study and agrees to allow access to all study-related documentation and information and be available for discussion about the study.

17. QUALITY CONTROL AND QUALITY ASSURANCE

Logic and consistency checks will be performed on all data entered into the eCRF or ultimately transferred into the database to ensure accuracy and completeness.

Training sessions, regular monitoring of the study at the study site by the Sponsor or designated personnel (eg, CRA), instruction manuals, data verification, cross checking, and data audits will be performed to ensure quality of all study data. Investigators' meetings and/or onsite study initiations will be performed to prepare Investigators and other study site personnel for appropriate collection of study data.

To ensure compliance with GCP and all applicable regulatory requirements, the Sponsor may conduct a quality assurance audit.

18. ETHICS

18.1. Ethics Review

The final study protocol, including the final version of the PIS-ICF and/or other patient information, must be approved or given a favorable opinion in writing by an IRB/IEC as appropriate. The Investigator must submit written IRB/IEC approval to Intercept before he or she can enroll any patient into the study. The Investigator is responsible for providing the IB and any other available safety information and information about payments and compensation available to study patients to the IRB/IEC for review.

The Investigator is responsible for informing the IRB/IEC of any amendment to the protocol in accordance with local requirements. A favorable opinion on amendments will be obtained prior to implementation, unless the amendment is necessary to reduce immediate risk to study participants. In addition, the IRB/IEC must approve all advertising used to recruit patients for the study. The protocol must be reapproved by the IRB/IEC upon receipt of amendments and annually, as local regulations require.

The Investigator is also responsible for providing the IRB/IEC with reports of any reportable serious adverse drug reactions from any other study conducted with the investigational product, according to local regulations and guidelines. The Sponsor will provide this information to the Investigator.

Progress reports and notifications of SARs will be provided to the IRB/IEC according to local regulations and guidelines. Investigators or the Sponsor or its designee will provide reports to the IRB/IEC as requested, as a minimum annually, and after the study is complete.

18.2. Ethical Conduct of the Study

The study will be performed in accordance with ethical principles that have their origin in the Declaration of Helsinki, “(64th World Medical Association [WMA] General Assembly, Fortaleza, Brazil, October 2013),” and are consistent with ICH/GCP, applicable regulatory requirements and the Sponsor’s policies.

18.3. Written Informed Consent

The Investigator(s) at each center will ensure that the patient is given full and adequate oral and written information about the nature, purpose, possible risk and benefit of the study. Patients must also be notified that they are free to discontinue from the study at any time. The patient should be given the opportunity to ask questions and allowed time to consider the information provided.

The patient’s signed and dated consent form must be obtained before conducting any study procedures.

The Investigator(s) must maintain the original, signed ICF. A copy of the ICF must be given to the patient.

18.4. Patient Confidentiality and Data Protection

All information obtained during the conduct of the study with respect to the patient will be regarded as confidential and confidentiality of all patients will be maintained. Monitors (eg, CRA, Medical Monitor), auditors and inspectors will require access to a patient's medical notes for the purpose of source document verification but the patient's confidentiality will be maintained at all times. An agreement for disclosure of any such information will be obtained in writing and is included in the statement of informed consent. The study data shall not be disclosed to a third party (with the exception of auditors and/or regulatory authorities) without the written consent of the Sponsor. All data shall be secured against unauthorized access.

The Investigator will maintain a list of patient's names and identifying information (eg, patient's hospital number, unique patient number). This list will not be collected by the Sponsor.

The PIS-ICF will explain that study data will be stored in a computer database, maintaining confidentiality in accordance with national data protection legislation. All data computer processed by the Sponsor or designee will be identified by unique patient number/randomization code/site number, only.

When personal data on patients are stored or processed by computer, the data must be protected to prevent disclosure to unauthorized third parties. The pertinent sections of the data protection laws in the country in which the protocol is being conducted will be complied with in full.

The PIS-ICF will explain that, for data verification purposes, authorized representatives of the Sponsor, regulatory authorities, or IEC/IRBs may require direct access to parts of the hospital or study site records relevant to the study, including patient's medical history.

19. INVESTIGATOR OBLIGATIONS

The Investigator or a medically trained designee will be responsible for obtaining written informed consent and for the care of the patients for the duration of the study. If the Investigator is not present in the study site during the assessment, he or she will leave instructions for the study site staff and a telephone number where he or she can be reached.

Named physician(s) will be responsible for the medical follow-up of patients, as applicable.

19.1. Adverse Event Reporting

The Investigator is responsible for recording AEs reported by the patient or discovered by any other means during the study. In agreeing to the provisions of this protocol, the Investigator accepts all legal responsibilities for immediate reporting of SAEs to the Sponsor.

